6.2. Secondary Objectives and Endpoints

Secondary Objectives	Study Endpoints
To determine the effect of TP-0184 on the treatment and the hematologic improvement of anemia in terms of hemoglobin increase, reduction in RBC transfusions and RBC Transfusion-Free \geq 8 weeks	
Response rate based on composite response criteria:
 
Hemoglobin increase \geq 1.5 g/dL maintained for a consecutive period of 8 weeks with no transfusions
 
OR
 
Reduction in units of \geq 4 RBC transfusions / 8 weeks (consecutive) compared with the pretreatment transfusion number in previous 8 weeks
 
OR
 
Patients who are RBC transfusion-free over any consecutive 8-week (56-day) period

To determine the effect of TP-0184 on the treatment and the hematologic improvement of anemia in terms of hemoglobin increase, reduction in RBC transfusions and RBC Transfusion-Free \geq 12 weeks	Response rate based on composite response criteria: Hemoglobin increase \geq 1.5 g/dL maintained for a consecutive period of 12 weeks with no transfusions OR Reduction in units of \geq 4 RBC transfusions / 12 weeks (consecutive) compared with the pretreatment transfusion number in previous 12 weeks OR Patients who are RBC transfusion-free over any consecutive 12-week (84-day) period
To measure time to RBC transfusion-free period	Time from first dose of TP-0184 to the first onset of a transfusion-free period for consecutive 8 weeks
To assess median duration of hemoglobin response	Duration of hemoglobin increase \geq 1.5 g/dL maintained for a consecutive period of $>$ 8 weeks with no transfusions.
To assess median duration of reduction in RBC transfusions (4 units / 8 weeks)	Duration of reduction in units of \geq 4 RBC transfusions / 8 weeks (consecutive)
To assess median duration of RBC-transfusion-free period \geq 8 weeks	Duration of RBC transfusion-free period
To assess progression to AML	Proportion of patients progressing to AML, time to AML progression
To assess overall survival	Time from first dose of TP-0184 to death due to any cause
To establish the PK profile of single agent TP-0184	PK parameters of TP-0184 as single agent: C_{max} , C_{trough} , t_{max} , AUC , and possibly others
Phase 2	

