8. SELECTION AND WITHDRAWAL OF PATIENTS

8.1. Inclusion Criteria

Each patient must meet the following criteria to be enrolled in this study:

1. A documented diagnosis of lower risk MDS (IPSS-R Low, Intermediate) according to WHO 2016 classification, de novo or secondary.
2. Bone marrow biopsy and/or aspirate performed pre-dose to assess disease status and available for review *prior* to full screening review. If the bone marrow biopsy and/or aspirate is nonproductive or nondiagnostic, the procedure must be repeated. Bone marrow biopsy/aspirate performed \leq 12 weeks prior to baseline will not need to be repeated if results and a minimum of 6 slides are available.
3. Relapsed, refractory/resistant, intolerant, or inadequate response to ESA treatment, as defined by the following:
 - Relapse according to IWG 2006
 - Refractory/resistant – documented non-response or response that is no longer maintained to prior ESA-containing regimen, either as single agent or combination (eg, with G-CSF). ESA regimen must have been either:
 - Recombinant human erythropoietin (rHu EPO) \geq 500 IU/wk for at least 8 doses or equivalent

OR

 - Darbepoetin alpha \geq 300 μ g Q3W for at least 4 doses or equivalent
 - Intolerant – documented discontinuation of prior ESA containing regimen, either as single agent or combination (eg, with G-CSF), at any time after introduction due to intolerance or an adverse event.
 - Inadequate response – in the absence of transfusions support, patients under ESA treatment for at least 12 weeks that do not show a rise in hemoglobin of greater than equal to 1 g/dl.
4. Patients with 5q deletions are allowed only if they have failed or are intolerant to lenalidomide treatment.
 - Failure or intolerance to lenalidomide defined as clinical and cytogenetic responses to according to the international working group 2006 MDS: (1) absence of response; (2) bone marrow progression during treatment with or without prior response; (3) secondary failure (loss of prior hematological response without bone marrow progression); or, (4) intolerance (treatment discontinuation due to AEs, with or without prior response) based on investigator judgement ([Prebet 2017](#)).
5. Previous treatment for anemia with or without RBC transfusion support:
 - a. Low transfusion burden (LTb), defined as requiring less than 4 red blood cell units in the 8 weeks before treatment (and baseline hemoglobin $<$ 9.0 g/dL)

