13.1.5. Analysis Datasets

The safety analysis set (SAS) is defined as all patients who receive at least one dose of study drug (TP-0184) and will be used for safety analysis and related time to event analyses if applicable.

The DLT analysis set (DAS) is defined as patients evaluable for the determination of dose escalation in Phase 1 who met either one of the following criteria:

1. Experienced a DLT during the first 28 days (the DLT evaluation period)
2. Completed the DLT evaluation period and received at least 80% of planned doses.

Patients who did not meet either of the above criteria are not evaluable for the dose escalation assessment and may be replaced as needed to permit dose escalation. The DAS will be used for DLT related analysis.

The efficacy evaluable analysis set (EAS) is defined as all patients who have baseline data of Hemoglobin value, number of transfusions received in previous 12 weeks before study treatment, have received at least 1 dose of TP-0184, and have at least 1 available post baseline response assessment as per the composite endpoint criteria. The EAS will be used for analyses of response rate and related efficacy analyses.

Pharmacokinetic evaluable analysis set is defined as all treated patients in the trial with sufficient and adequate PK sample data as determined by SDP Oncology.

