13.1.9.1. Efficacy Analysis

13.1.9.1.1. Phase 1 Efficacy Analysis

Phase 1 efficacy endpoints will be analyzed using Phase 1 Efficacy Analysis Set.

Efficacy analysis at Phase 1 will be conducted using similar methods defined in Phase 2 portion unless otherwise specified (details in [Section 13.1.9.1.2](#)).

Overall survival for Phase 1 is defined as the time from the date of initial dosing at same dose level or one dose level lower than RP2D to the date of death. Patients without documentation of death at the time of analysis will be censored at the date last known to be alive. Overall survival will be analyzed based on Phase 1 SAS patients.

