13.1.9.1.2. Phase 2 Efficacy Analysis

13.1.9.1.2.1. Response Rate

Response rate is defined as the proportion of patients who achieves response according to the composite endpoint criteria for a consecutive period of 8 weeks ([Appendix 1](#)). Response rate will be estimated with 2-sided 95% exact binomial confidence intervals based on EAS.

13.1.9.1.2.2.12-Week Response Rate

The 12-Week response rate is defined as the proportion of patients who achieves response according to the composite endpoint criteria for a consecutive period of 12 weeks ([Appendix 1](#)). The 12-Week response rate will be estimated with 2-sided 95% exact binomial confidence intervals based on the EAS.

13.1.9.1.2.3. Time to RBC transfusion-free analysis

Time to RBC transfusion-free period is defined as the time from the date of initial dosing at RP2D to first documentation of a transfusion-free period for patients who have one or more transfusion-free periods. Transfusion-free period is defined as the period that a patient becomes transfusion-free for consecutive 8 weeks or longer after treatment of TP-0184. Kaplan-Meier (K-M) survival curve and K-M median (estimate), along with 2-sided 95% CIs, will be provided.

13.1.9.1.2.4. Duration of Hemoglobin Response

Duration of hemoglobin response is defined as the time from the date of first documentation of a hemoglobin response to the date of first documentation of progression of hemoglobin response for hematologic responders. Hemoglobin response is defined as an increase ≥ 1.5 g/dL maintained for a consecutive period of > 8 weeks with no transfusions; hemoglobin progression is defined as a change from baseline < 1.5 g/dL of the hemoglobin or the start of one or more transfusions.

The K-M survival curve and K-M median (estimate), along with 2-sided 95% CIs will be provided.

13.1.9.1.2.5. Duration of Reduction in RBC Transfusion for 8 Weeks Analysis

High transfusion burden patient with reduction in RBC transfusion for 8 weeks is defined as high transfusion burden patients (baseline ≥ 4 U transfusions) patients with change from baseline of equal or more than 4 units transfusions in consecutive 8 weeks in EAS.

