The K-M survival curve and K-M median (if estimable), along with 2-sided 95% CIs will be provided.

13.1.9.1.2.11. Overall Survival

Overall survival is defined as the time from the date of initial dosing at RP2D to the date of death. Patients without documentation of death at the time of analysis will be censored at the date last known to be alive. Overall survival will be analyzed based on SAS patients whose initial dosing is RP2D.

The KM survival curve and K-M median (if estimable), along with 2-sided 95% Cis will be provided.

13.1.9.1.2.12. Hematopoietic Stem Cell Transplant Analysis

Hematopoietic stem cell transplant (HSCT) patients are defined as patients achieving a hematologic response and an HSCT in EAS. Summary statistics of the proportion of

hematopoietic stem cell transplant patients will be estimated with 2-sided 95% exact binomial confidence intervals among hematologic response in EAS.

13.1.9.1.2.13. MRI Imaging Analysis

Summary statistics will be provided based on MRI quantitative results by cohort, study, and overall patients. By-patient listings will be provided.

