20. APPENDICES

**APPENDIX 1. CONSIDERATION OF RESPONSE FOR COMPOSITE
ENDPOINT**

Patient population	Hemoglobin increase ≥ 1.5 in the absence of transfusion / 8 weeks	RBC transfusion free / 8 weeks	Reduction in units of ≥ 4 RBC transfusions / 8 weeks
High transfusion burden (≥ 4 U transfusion)	X	X	X
Low transfusion burden (1-3 U transfusion)	X	X	

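### Time to RBC transfusion-free is analysed by Kaplan-Meier only in patients who reach it, although the endpoint has no such restriction

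*Protocol*

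**What the plan says.** Protocol Section 6.2 defines the endpoint, for both phases, as "Time from first dose of TP-0184 to the first onset of a transfusion-free period for consecutive 8 weeks". SAP Section 1.2 repeats it for both phases. Neither limits it to patients who become transfusion-free.

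Protocol Section 13.1.9.1.2.3 sets the analysis. The time runs from initial dosing at the RP2D to "first documentation of a transfusion-free period for patients who have one or more transfusion-free periods", and a Kaplan-Meier curve and median with 95% confidence intervals follow. The section names no analysis set and gives no censoring rule. Section 13.1.9.1.1 extends the approach to Phase 1: "Efficacy analysis at Phase 1 will be conducted using similar methods defined in Phase 2 portion unless otherwise specified".

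Overall survival, in Section 13.1.9.1.2.11, is handled differently. It uses treated patients and states that "Patients without documentation of death at the time of analysis will be censored at the date last known to be alive".

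Three other passages bear on the point:

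- Inclusion criterion 5 in Section 8.1 reads "Previous treatment for anemia with or without RBC transfusion support". It defines low burden as "requiring less than 4 red blood cell units in the 8 weeks before treatment" together with baseline hemoglobin below 9.0 g/dL. Zero units is therefore allowed.
- Appendix 1 has only two rows: high burden (4 units or more) and "Low transfusion burden (1-3 U transfusion".
- Section 13.1.5 requires patients in the efficacy evaluable set (EAS), the denominator of the primary response rate, to "have at least 1 available post baseline response assessment as per the composite endpoint criteria". It does not say when such an assessment falls or how much follow-up makes one available.

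SAP Section 2 reports that the study was terminated after two patients and plans by-patient listings only. It does not revise any of these definitions.

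**The concern.** A time-to-reach endpoint should tell the reader both how soon and how often treated patients become transfusion-free. Limiting the analysed set to patients who succeed conditions on the outcome. It removes everyone who was treated and never got there, which is the information that Kaplan-Meier or cumulative incidence methods are designed to keep. The resulting median can look much the same for a drug that frees one patient in ten from transfusion and for one that frees six in ten. Because the output is a Kaplan-Meier curve and median, a reader may take it as describing the treated population.

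Two loose definitions affect the same analysis: which date counts as the event, and whether patients with no transfusions before treatment are in it. A similar but weaker question arises for the primary rate, where the EAS wording may leave early dropouts out of the denominator.

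**Working it through.** The plan states no figure for this analysis, so there is nothing to reproduce. The check has a general step and an illustration.

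**General step.** Let k patients reach the event and let d(t) be the number who have done so by time t. In the planned set there are no patients without the event, so nobody is censored and S(t) = (k − d(t))/k. This always ends at 0, and the median is the middle event time among the k. With all N treated patients followed to the end without dropout, S(t) = (N − d(t))/N. This ends at 1 − k/N, and a median exists only if k ≥ N/2.

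**Inputs.** N = 60 is the upper Phase 2 size (Protocol Section 7.1.3). Follow-up of 24 weeks is the planned treatment period (Section 7.3.1, Calculation of Dose). Assumed: all 60 are followed for 24 weeks with no death or dropout, and the k documentation times are evenly spaced from week 8 to week 24, both ends included. The i-th event is then at 8 + 16(i − 1)/(k − 1) weeks. The median is the first time at which S(t) ≤ 0.5.

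| Reachers k | Planned median (event k/2) | All-treated incidence at week 24 | All-treated median (event 30) |
|---|---|---|---|
| 6 | 8 + 16×2/5 = 14.4 weeks | 6/60 = 10% | not reached |
| 12 | 8 + 16×5/11 = 15.3 weeks | 12/60 = 20% | not reached |
| 36 | 8 + 16×17/35 = 15.8 weeks | 36/60 = 60% | 8 + 16×29/35 = 21.3 weeks |

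Incidence rises sixfold while the planned median moves by 1.4 weeks.

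**Different spacing.** Put onsets evenly inside weeks 0 to 16, with non-reachers censored at week 24. The median among reachers (mean of the two middle values) is 8.0 weeks whether 20%, 40% or 60% of patients reach. The all-treated median is not reached at 20% or 40% and is about 13.0 weeks at 60%.

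**Event date.** Section 6.2 and SAP Section 1.2 date the event at onset; Section 13.1.9.1.2.3 dates it at documentation. If documentation means completing the 8-week window, the dates differ by up to about 8 weeks. The planned medians above would become 14.4 − 8 = 6.4, 15.3 − 8 = 7.3 and 15.8 − 8 = 7.8 weeks. The protocol does not say that documentation means this.

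**Untransfused patients.** Criterion 5 admits patients with zero units in the 8 weeks before treatment, and Appendix 1 has no row for them. One who stays untransfused meets the event without any change in transfusion need. The documents do not say how many such patients were expected or how often they would start transfusion, so the effect cannot be sized.

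**EAS (secondary, conditional).** If m treated patients without a documented response are dropped, the rate goes from x/n to x/(n − m), which cannot be lower. If one post-baseline hemoglobin or transfusion record qualifies, m may be near zero, because Table 6 collects transfusion data continuously. If a full 8-week window is needed, early dropouts leave the denominator. Section 13.1.6 applies no imputation unless otherwise specified, and no text counts these patients as non-responders.

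**The case against.** The strongest defence is that the restricting clause only says when an event time exists, and that other patients would be censored as usual. The missing censoring rule alone does not refute this. Time to AML progression (Section 13.1.9.1.2.10) also has none, and nobody would read it as limited to progressors. Section 13.1 also leaves detailed methods to the SAP. But the AML analysis names the EAS and has no clause limiting it to patients with the event. Here the limiting clause is explicit, no wider set is named, and the SAP does not amend it. Even on the lenient reading, a censoring rule still has to be written.

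A second defence is that the plan shows elsewhere how many patients succeed. Part of this stands. Transfusion freedom is a component of the composite response, and Section 13.1.9.1.2.6 identifies patients with a transfusion-free period of at least 8 weeks. A reader might infer that the planned analysis cannot answer its objective at all. That goes too far, because the number of reachers would be visible from the set size. The harm is a median that invites misreading.

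Other strong inferences also fail. An 8-week date discrepancy is conditional on the meaning of documentation. That untransfused patients succeed almost automatically is unsupported: those in the low-burden group must have baseline hemoglobin below 9.0 g/dL and may start transfusion on study. That the EAS materially raises the chance of declaring success is also unsupported. The set is prespecified and tied to the composite criteria, the loss may be near zero, and no prior for the response rate is stated from which to compute such a chance.

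**Conclusion.** The main point holds with high confidence. As written, the analysis conditions on reaching the event and conflicts with the endpoint in Protocol Section 6.2 and SAP Section 1.2. That the curve falls to zero follows from the definition and needs no assumption. The sizes (14.4 to 15.8 weeks against not reached or 21.3 weeks) are illustrations that rest on 60 treated patients, complete 24-week follow-up and even spacing.

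The event-date mismatch is a real inconsistency of wording whose size depends on interpretation. The place of zero-unit patients is a real gap of unknown effect. The EAS remark is secondary: timing and minimum follow-up are unstated, exclusion on this ground can only raise the rate or leave it unchanged, and the effect may be nil.

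A reader might infer that published results are biased. The documents do not support this: SAP Section 2 reports termination after two patients and plans listings only. The text should be corrected before it is reused.

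**What to change.** 1. Analyse time to RBC transfusion-free in all patients treated at the RP2D, and by dose level in Phase 1. Censor those without the event at last transfusion follow-up.
2. State how death before the event is handled. Cumulative incidence with death as a competing event is one option.
3. Choose one event date, onset or documentation, define it, and use it in the endpoint tables and the analysis section alike.
4. Report the analysis also for patients transfused at baseline, and say where zero-unit patients belong in Appendix 1.
5. Keep a reachers-only median only if it is labelled descriptive and shown with the number reaching out of the number treated.
6. Define the timing and follow-up that make a response assessment available. Report the response rate also in all treated patients, counting no documented response as non-response.

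The cost is wording in the protocol and SAP. Table 6 already collects transfusion data continuously until 30 days after the last dose or the end-of-treatment visit, whichever is later. The 12 weeks of transfusion history required by inclusion criterion 6 identify patients transfused at baseline. The price in reporting is that the median will often be not reached and the all-treated response rate may be slightly lower.

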14. Platelet count $< 50,000/\mu\text{L}$ ($50 \times 10^9/\text{L}$) during screening.
15. Absolute neutrophil count (ANC) $< 500 / \mu\text{L}$ ($0.5 \times 10^9/\text{L}$) during screening.
16. Women who are pregnant or breastfeeding.

17. Male patients with partners of childbearing potential who are unwilling to use condoms in combination with a second effective method of contraception during the trial and for 7 months after the last administration of study treatment.
18. Inability to undergo MRI imaging.
19. Parenchymal iron overload by screening MRI.
20. Unwillingness or inability to comply with procedures required in this protocol.
21. Have undergone recent surgery with potential to cause the impairment of gastrointestinal tract absorption or that could cause short bowel syndrome with diarrhea due to malabsorption.
22. Have known hemochromatosis at baseline or a family history of hemochromatosis.
23. Presence of any psychological, familial, sociological or geographical condition that, in the opinion of the investigator, could potentially hinder compliance with the study protocol and follow-up schedule.
24. Any significant medical condition, laboratory abnormality, or psychiatric illness that would prevent the subject from participating in the study.
25. Live vaccines within 14 days prior to first study drug administration. COVID-19 vaccines (non-live) approved by regional health authorities are allowed.
26. Medications that are known strong to moderate CYP3A4 inducers must be discontinued at least 21 days prior to first dose of study drug. Medications that are known strong to moderate CYP3A4 inhibitors must be stopped 21 days (or 5 half-lives, whichever is shorter) prior to the first dose of study drug.
27. Patients who have received medications with known or possible risk of prolonging the QT interval or inducing Torsades de Pointes within the previous 7 days.

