Duration of reduction in RBC transfusions for 8 weeks is defined as the time from the assessment date of consecutive 8 weeks with reduction from baseline of RBC transfusions ≥ 4 units to the assessment date of the reduction from baseline < 4 units or increased transfusions frequencies from baseline within a consecutive 8 weeks. For high transfusion burden patient with reduction in RBC transfusion.

The K-M survival curve and K-M median (estimate), along with 2-sided 95% CIs will be provided.

13.1.9.1.2.6. Duration of RBC Transfusion-Free Period ≥ 8 weeks

RBC transfusion-free period ≥ 8 weeks patient is defined as a patient who maintains RBC transfusion-free during consecutive 8 weeks or longer in EAS.

Duration of RBC transfusion-free period ≥ 8 weeks is defined as the time from the assessment date of consecutive 8 weeks without any RBC transfusions to the assessment date of the first documented transfusion in the following visits for RBC transfusion-free period ≥ 8 weeks patients.

The K-M survival curve and K-M median (estimate), along with 2-sided 95% CIs will be provided.

13.1.9.1.2.7. Changes in Neutrophil Count

Hematologic improvement in neutrophil count (HI-N) is defined as patients achieving over any consecutive 8-week (56-day) period and / or decrease in neutrophil levels in EAS.

Change in neutrophils analysis will provide summary statistics of the proportion of patients with hematologic improvement in neutrophil count with 2-sided 95% exact binomial confidence intervals using EAS.

13.1.9.1.2.8. Changes in Platelet Count

Hematologic improvement in platelet count (HI-P) is defined as patients achieving hematologic improvement in platelets over any consecutive 8-week (56-day) period and / or decrease in platelet levels in EAS.

Change in platelet count analysis will provide summary statistics of the proportion of patients with hematologic improvement in platelet count with 2-sided 95% exact binomial confidence intervals using EAS.

13.1.9.1.2.9. Progression to AML

Progression to AML is defined follow the guidelines by IWG Response Criteria for MDS 2006 ([Appendix 6](#)).

Summary statistics of the proportion of patients progressing to AML will be estimated with 2-sided 95% exact binomial confidence intervals based on EAS.

13.1.9.1.2.10. Time to Progression to AML

Time to progression to AML is defined as the time from the date of initial dosing at RP2D to the date of first documented progression to AML using EAS.

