Survival	Endpoints: 
- Overall: death from any cause- Event free: failure or death from any cause- PFS: disease progression or death from MDS- DFS: time to relapse- Cause-specific death: death related to MDS

KEY: CR = complete remission; FAB = French-American-British; Hgb = hemoglobin; HI = hematologic improvement; IWG = International Working Group; MDS = myelodysplastic syndromes; PR = partial remission; PFS= progression-free survival; DFS= disease-free survival.

^a Dysplastic changes should consider the normal range of dysplastic changes (modification).

^b Modification to IWG (2000) response criteria.

Hematologic Improvement According to IWG Criteria (Cheson, 2006)	
Hematologic Improvement ^a	Response criteria (responses must last at least 8 week) ^b
Erythroid Response (HI-E) (pre-treatment, <11 g/dL)	
 - Hemoglobin increase by ≥ 1.5 g/dL - Relevant Reduction in units of RBC transfusions by an absolute number of at least 4 RBC transfusions/8 wk compared with the pretreatment transfusion number in the previous 8 wk
Platelet Response (HI-P) (pre-treatment, <100 X 10 ⁹ /L)	
 - Absolute increase of $\geq 30 \times 10^9$/L for subjects starting with $> 20 \times 10^9$/L platelets - Increase from $< 20 \times 10^9$/L to $> 20 \times 10^9$/L and by at least 100%^b
Neutrophil Response (HI-N) (pre-treatment, <1.0 X 10 ⁹ /L)	
 - At least 100% increase and an absolute increase $> 0.5 \times 10^9$/L^b
Progression or Relapse After HIC	
At least 1 of the following:
 
 - At least 50% decrease from maximum response levels in granulocytes or platelets - Reduction in Hgb by ≥ 1.5 g/dL - Transfusion dependence

KEY: HI-E = hematologic improvement erythroid response; HI-N = hematologic improvement neutrophil response; HI-P = hematologic improvement platelet response; IWG = International Working Group; RBC = red blood cell.

^a Pretreatment counts averages of at least 2 measurements (not influenced by transfusions, ie, no RBC transfusions for 2 weeks and no platelet transfusions for 1 week) ≥ 1 week apart (modification).

^b Modification to IWG (2000) response criteria.

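### The Section 13 definitions of HI-N and HI-P include a fall in the count, contrary to Appendix 6; separately, the EAS denominator dilutes a true improvement rate

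*Protocol*

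**What the plan says.** Protocol Section 13.1.9.1.2.8 defines HI-P as "patients achieving hematologic improvement in platelets over any consecutive 8-week (56-day) period and / or decrease in platelet levels in EAS". The statistic to be reported is the "proportion of patients with hematologic improvement in platelet count with 2-sided 95% exact binomial confidence intervals using EAS".

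Section 13.1.9.1.2.7 says that HI-N "is defined as patients achieving over any consecutive 8-week (56-day) period and / or decrease in neutrophil levels in EAS". The thing to be achieved is missing, so a decrease is the only event named. The statistic is the "proportion of patients with hematologic improvement in neutrophil count with 2-sided 95% exact binomial confidence intervals using EAS".

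Neither section gives a threshold or a duration for a decrease, reports a proportion with a decrease, or cites Appendix 6.

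Appendix 6 (IWG 2006) defines both responses as increases lasting at least 8 weeks. HI-P applies to pre-treatment platelets below 100 x10^9/L, and HI-N to pre-treatment neutrophils below 1.0 x10^9/L.

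The endpoint tables in the synopsis, in Sections 6.2 and 6.3 and in SAP Section 1.2 use similar wording, under objectives about changes in neutrophils and platelets.

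**The concern.** Two separate faults affect these proportions, and they act in opposite directions.

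- **Numerator.** If the definition is programmed as written, a patient whose platelets or neutrophils fall on treatment counts as improved. The proportion then mixes possible benefit with possible marrow toxicity and cannot be interpreted either way.
- **Denominator.** The EAS (Section 13.1.5) requires baseline hemoglobin and transfusion data, at least one dose and a post-baseline response assessment. It sets no condition on baseline platelets or neutrophils. Section 8.2 excludes only platelets below 50 and ANC below 0.5 x10^9/L, with no upper limit. Patients outside the scope of the Appendix 6 criteria therefore count as non-responders.

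At stake is the reading of two Phase 2 secondary endpoints. Phase 1 is affected too, because Section 13.1.9.1.1 applies similar methods there.

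**Working it through.** The documents give no expected rate, sample size or power for HI-N or HI-P, so there is no figure to reproduce. The texts are compared first, then the possible size is illustrated.

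**1. The texts side by side**

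| Feature | Sections 13.1.9.1.2.7 and .8 | Appendix 6 |
|---|---|---|
| Direction | Improvement and/or decrease; for HI-N only a decrease is named | Increase only |
| Size of change | Not stated | Platelets: rise of at least 30 x10^9/L if starting above 20. Neutrophils: rise of at least 100% and more than 0.5 x10^9/L |
| Duration | 8 weeks; not clear whether this covers the decrease | At least 8 weeks |
| Patients | EAS | Pre-treatment platelets <100 or ANC <1.0 x10^9/L |

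Appendix 6 also counts a fall of at least 50% from the maximum response in granulocytes or platelets as progression or relapse after improvement. Section 7.4.2 makes certain severe falls dose-limiting toxicities. Under the literal text, the same fall could be a relapse or a DLT and also an improvement.

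**2. How often would a stable count qualify through noise alone?**

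Assumptions, not from the documents: no drug effect; independent normal noise with SD 1; k later counts. The baseline B is the mean of two values, because Table 6 note i, Table 9 note a and Appendix 6 ask for at least two measurements. So B has mean 0 and variance 1/2, and given B each later count is lower with probability p = Φ(B).

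- *Any single lower value counts:* 1 − E[(1 − p)^k]. This gives 85% for k = 4, 94% for k = 8 and 97% for k = 12.
- *The fall must persist for about 8 weeks,* taken as r = 4 or 5 consecutive lower counts at two-week spacing: E[probability of a run of at least r in k trials with chance p], integrated numerically over B.

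| k | r = 5 | r = 4 |
|---|---|---|
| 5 | 11% | 19% |
| 12 | 27% | 38% |

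The result therefore runs from about 11% to about 97%, depending on rules that the text does not state.

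**3. Both effects in one example**

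Assumptions: 60 EAS patients (the Phase 2 maximum), 30 of them within the Appendix 6 limit, 6 true responders, and 20%, 50% or 80% of the other 54 showing a decrease. Intervals are exact 95%.

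| Calculation | Result |
|---|---|
| Appendix 6 responders among patients within the limit | 6/30 = 20.0% (7.7 to 38.6) |
| Appendix 6 responders in the EAS | 6/60 = 10.0% (3.8 to 20.5) |
| Literal definition, 20% decrease: 6 + 11 | 17/60 = 28.3% (17.5 to 41.4) |
| Literal definition, 50% decrease: 6 + 27 | 33/60 = 55.0% (41.6 to 67.9) |
| Literal definition, 80% decrease: 6 + 43 | 49/60 = 81.7% (69.6 to 90.5) |

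With no true responder, the literal definition still gives 12/60, 30/60 or 48/60, that is 20%, 50% or 80%.

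The dilution depends on the share above the limit. If 25%, 50% or 75% of the 60 are above it, the rate among patients within the limit is 6/45 = 13.3%, 6/30 = 20% or 6/15 = 40%, against 10% in the EAS.

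**The case against.** The strongest reply is that this is a drafting slip. In the endpoint tables the labels HI-N and HI-P attach to the improvement only, and the decrease follows as a second outcome under an objective about changes in the count. The reported statistic in Section 13 names improvement alone, and Appendix 6 leaves no doubt about direction. This reading is plausible and probably what was meant. It does not repair Section 13, which puts the decrease inside each definition, leaves the HI-N sentence incomplete and provides no separate analysis of decreases.

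A second reply is that the two faults rest on incompatible readings: if Appendix 6 governs, decreases do not count; if it does not, there is no pre-treatment limit. That is fair, and the two should not be added together. But each reading leaves one fault. The literal text has the wrong numerator, and the Appendix 6 reading has a denominator that includes patients outside its scope.

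A third reply stands in full: marrow toxicity would not be hidden. Section 13.1.9.2.2 already plans CTCAE shift tables to the worst post-baseline value and laboratory summaries over time.

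**Conclusion.** The definitions are wrong as written and should be corrected. Read literally, they score a fall as improvement, against the protocol's own Appendix 6. The size cannot be fixed from the documents. Under the noise model it is about 11% to 38% of stable patients if the fall must persist for about 8 weeks, and about 85% to 97% if one lower value is enough. The dilution by the EAS is separate; the halving from 20% to 10% rests on the assumed half of patients above the limit.

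A reader might infer more than the documents support:

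- *That the improvement rate would be 80% to 90% or more without any drug effect.* This is the extreme case. It needs any single lower value to qualify, and the text is silent on that.
- *That the denominator adds to the inflation, or is all patients.* It is the EAS, and it lowers an improvement rate.
- *That the trial's main conclusion or its reported results are affected.* The primary endpoint does not use these definitions. SAP Section 2 states that the study is terminated after two patients and plans by-patient listings only, so no HI-N or HI-P rate is among the planned outputs. The point bears on the protocol's plan and on any reuse of its text.

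**What to change.** - In Sections 13.1.9.1.2.7 and 13.1.9.1.2.8, define HI-N and HI-P by reference to Appendix 6, including its 8-week duration, and remove the decrease from both definitions.
- Report each proportion, with an exact 95% CI, among EAS patients who meet the Appendix 6 pre-treatment limit (ANC <1.0 or platelets <100 x10^9/L). Show the whole-EAS rate alongside if wanted, labelled as such.
- Report decreases separately in the safety analysis set, through the CTCAE shift tables already planned in Section 13.1.9.2.2. Section 13.1.9.2.1 names no such tables for Phase 1, so extend them there. If a proportion with a decrease is also wanted, state its threshold and duration.
- Align the endpoint wording in the synopsis, Sections 6.2 and 6.3, and SAP Section 1.2.

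The cost is wording and some precision. In the example the exact interval widens from 16.7 points (3.8 to 20.5, n = 60) to 30.9 points (7.7 to 38.6, n = 30). No additional data are needed.
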